Specific Aim 1 (Primary Aim): To determine the effectiveness of ZNS treatment in reducing drinking on the primary outcome measure: drinks per week (measured using the Timeline Followback Method), for eight weeks at a target dose of 600 mg of ZNS daily for 160 heavy-drinking, alcohol-dependent veterans. We hypothesize that ZNS treatment will reduce the heavy drinking days per week and the total drinks per week significantly more than the placebo and that the benefits will persist at three months follow-up after treatment.

Specific Aim # 2 (Secondary Aim): To examine the effects of ZNS treatment on heavy drinking days per week, , percentage of subjects with no heavy drinking days (PSNHDD) the urge to drink (craving), biomarkers of alcohol intake, clinical global impression, medication tolerability, and other patient-centered outcomes. We hypothesize that ZNS will demonstrate significantly greater improvements than the placebo on these measures by the treatment endpoint as well as at follow-up.

Specific Aim #3 (Secondary): To use telephone-based daily process data collection to elucidate the mechanism of action of ZNS as it relates to changes in craving, anxiety, and genetic variation. *This method has been shown to elucidate the mechanism of action of topiramate, as well as its pharmacogenetic interactions.* We hypothesize that ZNS' effects will be moderated by genetic variation, craving, and anxiety, but mediated through changes in self-efficacy to reduce heavy drinking.

Specific Aim #4 (Exploratory): The exploratory aim is to examine the pharmacogenetic interactions between ZNS and the therapeutic response. We hypothesize that both the long (L) allele of the VNTR polymorphism in exon 3 of the *DRD4* gene and the CC genotype of the *DBH* rs1611115 (C-1021T) SNP will show a pharmacogenetic effect with ZNS, as evidenced by a greater reduction in drinking than for the short (S) allele and T carriers respectively.

Specific Aim #5 (Exploratory) To compare ZNS and placebo-treated subjects on pre- and post-treatment changes in measures of stress-reactivity (i.e., stress-induced anxiety, alcohol craving, autonomic nervous system activity), cue-elicited craving, and impulsivity. We hypothesize that ZNS will attenuate stress-reactivity, cue-elicited craving, and impulsivity more than placebo in a stress laboratory paradigm, and that attenuation of those measures will be associated with reduction in drinking.

4. BACKGROUND:

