Specific Aims 1- 5, Effectiveness of ZNS in the Treatment of Alcohol-Dependent Veterans: We propose to conduct a 16 week, randomized, double blind, placebo-controlled study of ZNS in **N=160** regularly heavy drinking veterans with AD in the context of a minimal ambulatory psychosocial treatment aimed at enhancing adherence to medication (Medical Management, MM), (68). We will recruit and enter **160** subjects with which the study will be adequately powered. *All subjects must be currently alcohol dependent. The target dosage for ZNS is 500mg/day, which will be titrated up over the first 7 weeks of treatment, with dosage increases based on tolerability. The titration schedule will start with 100mg daily, increased to 200mg/day after the first week,*

and then increased by 100mg/day every 2 weeks to the **target dose of 500mg/day**. Subjects will then begin 9 weeks at the target dose with the option to increase to 600mg daily after two weeks at target if treatment response is suboptimal and there are no significant side effects (no current moderate to severe AE's with 500mg daily). Dosing will remain flexible with respect to the time of day that the medication is administered, in order to maximize compliance and minimize the impact of adverse effects. The dosage will be held or reduced based on the appearance of moderate-to-severe adverse effects. **Following the seven week titration phase, subjects will begin the 9 week period of active treatment on the target dose, followed by up to 2 weeks of tapering and discontinuation of the medicine, and a return for follow-up at three months post-treatment. The dosing is also flexible in that it will allow subjects to continue on at less than the target dose based on tolerability, but subjects must be able to tolerate at least 200mg/day (two pills). Also, if subjects are not having moderate to severe side effects during the treatment phase, and have not yet reached 600mg/day, they may be increased by up to 100mg every 2 weeks if it is felt that they may benefit further from it. This will allow maximum flexibility and optimal dosing.**

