6.D.2. Visit 1 (Baseline Visit): N= 160 subjects will be randomly assigned to receive either ZNS (80 subjects) or placebo (80 subjects). We will use blocked stratified randomization with treatment site (VA Connecticut versus Bedford) and the use of other psychotropic medications (e.g., antidepressants) as the stratification variables, with block sizes of 4 in each stratum to achieve treatment balance throughout the randomization process. Within 21 days after the screening visit, eligible subjects undergo a two-hour pre-treatment assessment (described below). At the baseline visit, subjects will complete a packet of questionnaires. Subjects will receive their first medication management session and first supply of study medication during a treatment session (visit 1) scheduled on the same day, following completion of the baseline assessments.

Subjects will begin study medication (i.e., ZNS or matching placebo) at an initial dosage of 100mg/day. All subjects will be asked to bring any remaining capsules and the study medication container to their next and all subsequent clinic visits, so that capsule counts can be used to measure compliance. The subject begins 6-week titration phase, during which the dosage will be titrated up as indicated above and in Table 1. Subjects will be paid a nominal but fair amount of money in compensation for all visits, including follow-up visits. Table 1 shows the titration schedule:

TABLE 1: Medication Titration Schedule

Week	Placebo	Zonisamide dose
1	One capsule daily	100mg QHS
2	Two capsules daily	200mg QHS
3	Two capsules daily	200mg QHS
4	Three capsules daily	300mg QHS
5	Three capsules daily	300mg QHS
6	Four capsules daily	400mg QHS
7	Four capsules daily	400mg QHS
8-9	Five capsules daily	500mg QHS (Target dose)
10-16	Five or Six capsules daily, 7 weeks duration	Continue 500mg daily or optional increase to 600mg QHS, 7 weeks duration
17-18	TAPER: Decrease capsules by one a day every 3 days, over a period of up to 15 days	TAPER: Decrease dose 100mg every 3 days, over a period of up to 15 days

Table 1 notes: 7 weeks of titration to the 500mg daily target dose. 9 weeks at the target dose with the option to increase to 600mg daily after two weeks at target if treatment response is suboptimal and there are no significant side effects (no current moderate to severe AE's with 500mg daily).

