We will use the percentage of subjects with no heavy drinking days (**PSNHDD**) as the primary outcome variable. This outcome is the FDA recommended endpoint for pivotal trials, and is described in Falk et al., (2010). The PSNHDD can be derived from each subject's TLFB data. An important initial consideration in considering effectiveness will be to identify baseline differences between groups that may have occurred despite randomization. **Successful outcomes during the treatment trial will be defined in terms of a statistically significant difference on the primary outcome measure: PSNHDD, compared during the 8 weeks of active treatment at the target dose, allowing for a 6 week grace period for the medication titration.** For all analyses, heavy drinking days will be defined as follows; for men > 5 drinks in a day and for women > 4 drinks in a day. Patients will be followed irrespective of whether they continue to receive medication treatment, so that analysis will include all data available for the 8-week treatment period. The analysis will be **intent-to-treat**, and dropouts will be considered as having relapsed to heavy drinking. We will use a logistic regression analysis with PSNHDD as a categorical dependent variable. Medication condition (placebo or ZNS) will be the main independent variable, and we will include the variables of early onset of alcoholism (EOA, binary), and the use of additional psychotropics (e.g., antidepressants, a binary variable) as covariates. The α will be set at .05 for the primary outcome variable. Between site differences will be explored.

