Additionally, participants can earn up to \$320 for completing the IVR phone calls (\$2 per completed phone call plus \$6 for each week where 6 or more calls are completed (up to \$20/week for 16 weeks)). If they do not have a cell phone to complete the calls we will give them one to borrow during the study which must be returned when they complete the study.

By participating in the stress labs, subjects can also earn \$40 for the script development, \$100 for each of the two stress labs (\$200 total), and up to \$40 for the computer tasks during the stress labs (up to \$20 per lab session).

If all parts of this study are completed, participants have the potential to earn up to \$1645 (this does not include the additional travel compensation mentioned earlier). This payment is for the time and effort associated with study assessments and procedures.

The alcohol clinical trials unit staff at both the West Haven VAMC and the Bedford site have considerable experience in administering questionnaires and diagnostic assessments, as well as with protecting that data appropriately.

Payments for screening, outpatient visits and follow up will be made through electronic funds transfer (EFT). Participants will need to provide us with your banking information by completing a special payment form. Alternatively, if participants do not have a bank account, a check will be mailed to them instead. This check(s) will be mailed to the address they provide us with. Alternatively, patients may choose to receive gift certificates issued to them for use at the VCS canteen (retail store) or VCS cafeteria here at the VACHS. Study payments are subject to withholding for outstanding federal debts (i.e., defaulted student loans, interstate child support, back taxes etc) without notification.

Payment for participation in IVR phone calls and Stress labs *will be given in the form of cash at the time of the subjects participation.*

TABLE 5: Subject visit and payment overview:

Visit title	Visit #	Weeks completed on medication	Payment (US \$)
Screening	0	0	50
Baseline (start meds)	1	0	65
Regular visit (1 week after last)	2	1	50
Regular visit (1 week after last)	3	2	50
Regular visit (1 week after last)	4	3	50
Regular visit (1 week after last)	5	4	50
Regular visit (1 week after last)	6	5	50
Regular visit (1 week after last)	7	6	50
TARGET dose 500mg (regular weekly visit, 1 week after last))	8	7	50
Regular visit (1 week after last)	9	8	60
Regular visit (1 week after last)	10	9	50

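### The primary outcome has no fixed scoring window: three different eight-week windows can be read from the plan, and none satisfies every statement in it

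*Combined protocol and SAP*

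**What the plan says.** **Primary analysis.** Section 6.I.2 defines trial success as a significant difference on PSNHDD, "compared during the 8 weeks of active treatment at the target dose, allowing for a 6 week grace period for the medication titration". The same section repeats the eight-week length but never names the weeks.

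**Seven weeks of titration.** Section 6.A says: "Following the seven week titration phase, subjects will begin the 9 week period of active treatment on the target dose". The notes to Table 1 say "7 weeks of titration to the 500mg daily target dose", and the table puts weeks 6-7 at 400 mg and weeks 8-9 at 500 mg. Table 5 labels visit 8, with 7 weeks completed on medication, "TARGET dose 500mg (regular weekly visit, 1 week after last".

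**Six weeks of titration.** The running text of 6.D.2, just above Table 1, says: "The subject begins 6-week titration phase". Section 6.H.1 implies the same: it schedules the second stress lab after at least two weeks at target and gives that as weeks 9-16.

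**Other analysis text.** For the secondary outcomes, 6.I.2 ties the grace period to however long titration takes and again uses eight weeks at target. Section 6.I.4 uses the final eight weeks of treatment and states that this agrees with the Aim 1 analyses.

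**Specific Aims.** Aim 1 sets out to show an effect "on the primary outcome measure: drinks per week (measured using the Timeline Followback Method), for eight weeks at a target dose of 600 mg". Aim 2 lists "percentage of subjects with no heavy drinking days (PSNHDD) the urge to drink (craving" among the secondary measures. In Table 1 the 600 mg step is optional and covers weeks 10-16 only: "Continue 500mg daily or optional increase to 600mg QHS, 7 weeks duration".

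**The concern.** The rule for scoring the primary outcome contradicts the plan's own schedule. Under Table 1, a six-week grace period followed by eight weeks takes in a titration week. An analysis of eight weeks wholly at target has to start later.

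This matters because PSNHDD is all-or-nothing. A single heavy day in a week that only some readings include turns a success into a failure. The same drinking records can therefore give different results on the outcome that 6.I.2 uses to define success. While the window is open, it can also be chosen after the data have been seen.

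**Working it through.** **1. Windows, by week arithmetic**

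| Reading | Source | Weeks | Target-dose weeks under Table 1 |
|---|---|---|---|
| 6-week grace, then 8 weeks | 6.I.2, primary | 7-14 | 7 of 8 |
| Grace equal to titration (7 weeks), then 8 weeks | 6.I.2, secondary, with Table 1 | 8-15 | 8 of 8 |
| Final eight of 16 weeks | 6.I.4 | 9-16 | 8 of 8 |

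Weeks 9-14 are common to all three; weeks 7, 8, 15 and 16 are in dispute. Weeks 7-14 miss the target-dose condition under Table 1. Weeks 8-15 do not have a six-week grace period and disagree with 6.I.4. Weeks 9-16 agree with 6.I.4 but imply an eight-week grace period.

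**2. The plan's own power figure**

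Inputs: 80 per arm (6.D.2); 12 and 7 pilot subjects without relapse (6.I.6); pilot N = 40 (Specific Aims). The pilot arm sizes are not given; 20 per arm is assumed, so 12/20 = 0.60 and 7/20 = 0.35. The test is taken as two-sided at 5%.

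- Pooled SE = √(2 × 0.475 × 0.525 / 80) = 0.0790
- Unpooled SE = √((0.60 × 0.40 + 0.35 × 0.65) / 80) = 0.0764
- Power = Φ((0.25 − 1.96 × 0.0790) / 0.0764) = 89.4%, matching the stated figure of more than 89%.

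**3. How many subjects change status (illustration only)**

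The documents give no weekly rates. Assume that each subject has a constant weekly risk r of at least one heavy day, with no dropout. Let r vary between subjects by a beta distribution with within-subject correlation ρ. Its mean is set so that E[(1−r)^8] is 0.60 (zonisamide) or 0.35 (placebo).

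For two eight-week windows k weeks apart, the share of subjects who succeed in one but not the other is 2 × {E[(1−r)^8] − E[(1−r)^(8+k)]}. Multiply by 80 per arm and add the arms.

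| | ρ = 0 | ρ = 0.3 | ρ = 0.7 |
|---|---|---|---|
| 8-15 vs 9-16 (k = 1), discordant share, zonisamide / placebo | 0.074 / 0.086 | 0.034 / 0.039 | 0.015 / 0.016 |
| Subjects of 160 | 12.8 | 5.9 | 2.5 |
| 7-14 vs 9-16 (k = 2), discordant share, zonisamide / placebo | 0.144 / 0.162 | 0.064 / 0.073 | 0.028 / 0.031 |
| Subjects of 160 | 24.4 | 11.0 | 4.7 |

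ρ = 0 is an extreme in which everyone in an arm has the same risk.

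**4. Effect on the test (simulation)**

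40,000 trials per setting, pooled z-test, no covariates, Monte Carlo error at most about 0.2 percentage points.

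| | ρ = 0 | ρ = 0.3 | ρ = 0.7 |
|---|---|---|---|
| Verdict differs, 8-15 vs 9-16 | 9% | 6% | 4% |
| Verdict differs, 7-14 vs 9-16 | 12% | 8% | 5% |
| No drug effect (35% in both arms), best of three windows significant | 10% | 8% | 7% |

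Power is about 89% for each eight-week window. The expected treatment difference is the same in all three, which follows from the constant-risk assumption.

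**5. Dropout counted as relapse**

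Suppose 20% drop out early in each arm and overall success stays at 60% and 35%. The 64 who remain per arm then succeed at 0.60/0.80 = 0.75 and 0.35/0.80 = 0.4375. At ρ = 0:

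- k = 1: 2 × 64 × [(0.75 − 0.75^1.125) + (0.4375 − 0.4375^1.125)] = 128 × (0.0265 + 0.0430) ≈ 9 subjects, down from 13.
- k = 2: 2 × 64 × [(0.75 − 0.75^1.25) + (0.4375 − 0.4375^1.25)] = 128 × (0.0520 + 0.0817) ≈ 17 subjects, down from 24.

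**The case against.** **Section 6.I.4 may already answer the question.** It is the only passage that places an eight-week analysis window within the 16 weeks, and it ties that window to Aim 1. On this view the six-week wording in 6.I.2 is merely out of date. This has weight, and it is a good reason to adopt weeks 9-16. It does not settle the matter: 6.I.2 is the section that governs the primary outcome, its six-week grace period does not lead to week 9, and 6.D.2 and 6.H.1 also point to six weeks of titration.

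**The count should not be inflated.** A reader might add weeks 8-16, or even 7-16, and claim four or five windows. The documents do not support that. Every analysis statement says eight weeks; 8-16 is nine weeks long and 7-16 is ten. Only 8-15 and 9-16 are both eight weeks long and wholly at target under Table 1.

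**The largest figures are not typical.** The 24 subjects and 12% come from the widest pair of windows, zero correlation and no dropout. Early dropouts fail under every window and cannot be reclassified, so the plan's own dropout rule shrinks the effect. The false-positive figures require someone to pick the window after seeing results. Nothing in the documents says that anyone intends to.

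**If drinks per week is primary, the one-day mechanism largely disappears.** That is true, but 6.I.2 uses the same unnumbered eight weeks for that outcome, so the window still has to be stated.

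**Conclusion.** The point holds. The primary scoring rule in 6.I.2 conflicts with the dosing schedule in 6.A, Table 1 and Table 5 and with the window in 6.I.4. It cannot be programmed in only one way.

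The conflict itself rests on the text alone. The sizes rest on the assumptions listed above: for the two windows wholly at target under Table 1, about 13, 6 or 3 reclassified subjects and a changed verdict in about 9%, 6% or 4% of trials, less with early dropout.

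A reader might infer that the ambiguity favours zonisamide or costs power. The documents do not support either reading. The ambiguity applies to both arms alike, and the power calculation is the same for any eight-week window because the pilot rates carry no stated window. What is at stake is the reproducibility of the primary result and protection against a choice made after the data are seen.

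The Specific Aims add a related contradiction: they name a different primary outcome, and their eight weeks at 600 mg exceed the seven weeks that Table 1 allows for that dose.

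**What to change.** In 6.I.2, replace the grace-period wording with a window stated by study week. For example: *PSNHDD is scored over weeks 9-16 (days 57-112, day 1 being the baseline visit) for every subject in both arms, whatever dose was reached.* The days follow from 8 × 7 + 1 = 57 and 16 × 7 = 112. Fix this before unblinding and use the same window for the secondary drinking outcomes in 6.I.2.

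Weeks 9-16 agree with 6.I.4 and lie within the scheduled target-dose weeks whether titration is taken as six weeks (target 7-16) or seven (target 8-16). The analysis window therefore need not wait for the titration text to be settled.

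The window change costs one sentence and a cross-reference. No new data, visits or subjects are needed, because the weekly Timeline Followback records every day. The downside is that week 8, a target-dose week in Table 1, goes unused for this outcome. Weeks 8-15 would use it but would disagree with 6.I.4.

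Two further text corrections are needed. Name one primary outcome in both the Specific Aims and 6.I.2. The sponsor must also reconcile the six- and seven-week titration passages and the 500 mg and 600 mg target passages; this review takes no position on which is right.

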Daily reports obtained using IVR will be used to identify subjective correlates of medication effects (e.g., craving) and to monitor medication use. A half-day long "stress response" laboratory session based on that developed by (69) will be performed with subjects, if their schedule allows, after screening but before starting medication (baseline stress/impulsivity), and then a second lab will be performed between weeks 8-16.

6.B. Subjects and recruitment: The study is being conducted at two sites; (1) the West Haven VAMC, also known as VA Connecticut Healthcare System (VACHS), at our Alcohol Research Center (VAARC); and (2) the Bedford VAMC in Massachusetts. We have had successful collaborations between these two sites previously, and both have good records of subject recruitment.

6.C. Inclusion and Exclusion Criteria: N=160 men and women **veterans** are being recruited through referrals, flyers at VA facilities, and from among participants in prior studies in the VAARC. Each subject must meet all of the following **inclusion criteria** to participate: a) age 21-70 years, inclusive; b) regular heavy drinkers as defined by averaging 1 heavy drinking days per week over 90 days baseline pre-treatment timeline follow-back (TLFB), and **current DSM-IV-TR alcohol dependence** that recognize a need to reduce or stop drinking (**Note:** heavy drinking days will be defined as follows; for men greater than or equal to 5 drinks in a day and for women greater than or equal to 4 drinks in a day); c) women of child-bearing potential (i.e., no hysterectomy, bilateral oophorectomy, or tubal ligation or <2 years postmenopausal), must be non-lactating, practicing a reliable method of birth control, and have a negative serum pregnancy test prior to initiation of treatment; d) willingness to provide signed, informed consent to participate in the study.

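### Heavy drinking days are defined inclusively for entry (5 or more drinks for men, 4 or more for women) but, as printed, strictly for every analysis (more than 5, more than 4), so days exactly at the cut change status between eligibility and PSNHDD

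*Combined protocol and SAP*

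**What the plan says.** Section 6.C, inclusion criterion b, defines a heavy drinking day in words: "for men greater than or equal to 5 drinks in a day and for women greater than or equal to 4 drinks in a day". It selects "regular heavy drinkers as defined by averaging 1 heavy drinking days per week over 90 days baseline" on the timeline follow-back (TLFB).

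Section 6.I.2 sets the outcome: "We will use the percentage of subjects with no heavy drinking days" (PSNHDD), "compared during the 8 weeks of active treatment at the target dose". The same paragraph gives the cut: "For all analyses, heavy drinking days will be defined as follows; for men > 5 drinks in a day and for women > 4". It also says that "dropouts will be considered as having relapsed to heavy drinking", and "The α will be set at .05 for the primary outcome variable".

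No section explains a change of cut between entry and analysis. The only other use of the 5-drink level, exclusion criterion m in 6.C, is also inclusive. The status of PSNHDD is itself unsettled: Specific Aim 1 names drinks per week as primary and Specific Aim 2 lists PSNHDD as secondary, whereas 6.I.2 and 6.I.6 call PSNHDD primary.

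**The concern.** The two rules agree on every day except one of exactly 5 drinks (men) or 4 (women). That exception matters because PSNHDD is all-or-nothing: one heavy day in 8 weeks makes a participant a failure. The cut therefore decides the outcome for every completer whose heaviest day lies exactly on it. As printed, such a person is reported as free of heavy drinking while showing drinking that the trial itself calls heavy when it enrols people.

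The 6.I.2 rule is the only definition in the statistical section and it governs all analyses, so it also reaches heavy drinking days per week and PSNHDD at the three-month follow-up. An analyst would program what is printed. If the conflict stays open until data are available, the choice of cut for a binary endpoint could be made with results in view. The power statement is also affected, because the documents do not say which cut produced the pilot counts behind it.

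**Working it through.** **1. The two definitions side by side**

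| Drinks in the day | Entry rule (6.C) | Analysis rule as printed (6.I.2) |
|---|---|---|
| Men 4 or fewer; women 3 or fewer | not heavy | not heavy |
| Men exactly 5; women exactly 4 | heavy | not heavy |
| Men 6 or more; women 5 or more | heavy | heavy |

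Limiting example: a man at exactly 5 drinks every day has 7 heavy days per week under 6.C, against a requirement of 1. Over 8 × 7 = 56 days he has 56 heavy days under the 6.C rule (failure) and 0 under the printed 6.I.2 rule (success), at 5 × 7 = 35 drinks per week in both cases.

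**2. Reproducing the stated power**

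Inputs: 12 ZNS and 7 placebo pilot subjects without relapse (6.I.6); pilot N = 40 (Section 3); 80 per arm (6.D.2, 6.I.6); α = 0.05 (6.I.2). Assumptions: 20 pilot subjects per arm, giving 60% and 35%, and a two-sided test.

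Formula (pooled variance, no continuity correction): power = Φ{[(p1 − p2) − 1.96 × SE0] / SE1}.

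- SE0 = √(2 × 0.475 × 0.525 / 80) = 0.0790
- SE1 = √[(0.60 × 0.40 + 0.35 × 0.65) / 80] = 0.0764
- Power = Φ(1.246) = 89.4%

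This agrees with the stated figure of more than 89%. At 64 per arm the same formula gives 81.6%; the stated 76% fits a continuity-corrected (76.4%) or Fisher exact (75.6%) calculation, so the two stated powers come from different methods. That does not affect this point.

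**3. Equal share of failures at the cut**

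Suppose 60% and 35% are the rates under the inclusive rule, and a share f of failures in each arm is at the cut and becomes a success under the printed rule. Then ZNS = 0.60 + 0.40f, placebo = 0.35 + 0.65f, and gap = 0.25(1 − f).

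| f | ZNS | Placebo | Gap (points) | Power, 80 per arm |
|---|---|---|---|---|
| 0 | 60.0% | 35.0% | 25.0 | 89.4% |
| 5% | 62.0% | 38.3% | 23.8 | 85.9% |
| 10% | 64.0% | 41.5% | 22.5 | 82.0% |
| 20% | 68.0% | 48.0% | 20.0 | 73.1% |

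The documents give no value for f. These rows show sensitivity and are not estimates.

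**4. Unequal shares**

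Gap = 0.25 + 0.40 × f(ZNS) − 0.65 × f(placebo). It widens when f(ZNS) exceeds 0.65 / 0.40 = 1.625 times f(placebo). For example, 20% and 5% give 68.0% vs 38.3%, a gap of 29.8 points.

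**5. Dropouts**

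Dropouts fail under both rules, so only failures among completers can be reclassified. Assume, for illustration, that 20% of each arm drops out. Movable failures are then 40 − 20 = 20 points (ZNS) and 65 − 20 = 45 points (placebo). The 20% row of the table would need 0.20 × 40 / 20 = 40% of ZNS and 0.20 × 65 / 45 = 29% of placebo completer failures to lie exactly at the cut. If instead 10% of completer failures in each arm are at the cut, the rates are 60 + 2.0 = 62.0% and 35 + 4.5 = 39.5%. The rates rise less than in the table, and the gap is again 22.5 points.

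**The case against.** **The sign may be an artefact.** The point rests on one character. The wording around the cut in 6.I.2 closely follows 6.C, and both inclusive statements in 6.C are in words, so an inclusive cut was probably meant. The ≥ could have been lost in typing or in reading the PDF. This stands as a reason for lower certainty and severity. If the source prints ≥, confirmation is all that is needed. It does not remove the conflict in the text as it reads.

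**Heavy drinking days per week.** A reader might infer that this outcome would appear to fall from its entry value with no change in drinking. The documents do not support that. The 6.I.2 cut applies to all analyses, and the mixed model in 6.I.2 adjusts for pre-treatment drinking, so baseline and on-treatment values would be scored alike. The entry count serves only as an eligibility screen.

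**Direction of effect.** A reader might also infer that the printed cut necessarily dilutes the treatment effect, or that it favours ZNS. Neither follows. Dilution requires similar shares at the cut in both arms; a drug that lowers peak intake could produce unequal ones. The same cut applies to both randomised arms, so the test remains valid under the null.

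**Rarity and recoverability.** The 5-a-day man is an extreme case: he must never reach 6 in the window and must not drop out. TLFB holds daily quantities, so either cut can be computed later. Drinks per week, which Specific Aim 1 names as primary, does not depend on the cut. All of this is fair and limits the stakes, but the published definition of PSNHDD is still inconsistent with the entry definition.

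**Conclusion.** The inconsistency is real in the current text. As printed, completers whose heaviest day in the 8-week window is exactly 5 drinks (men) or 4 (women) count as having no heavy drinking, although 6.C would call that day heavy. Compared with the inclusive rule, PSNHDD can only rise or stay the same in each arm, by an amount that cannot be estimated from the documents. The effect on the difference between arms is unknown in size and direction. The fall to 22.5 points and about 82% power at a 10% share holds only under the stated assumptions: 20 pilot subjects per arm, pilot counts scored inclusively, and equal shares at the cut. Because the sign may be a lost ≥, this is best treated as a threshold to correct or confirm before analysis, without concluding that a looser endpoint was chosen deliberately.

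**What to change.** In 6.I.2, replace the cut with 5 or more drinks in a day for men and 4 or more for women, or confirm that the source document already prints ≥. State that this one definition applies to eligibility, the pre-treatment value, PSNHDD (on treatment and at follow-up) and heavy drinking days per week. In 6.I.6, state which cut was used to score the pilot's 12 and 7; if it was not the inclusive one, recompute the power.

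The cost is one line of wording and one check of the pilot data. TLFB already records drinks for each day (6.F.2), so data collection does not change. The downside is that observed success rates in both arms may be slightly lower than under the printed cut.
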